## Secondary

- To determine if a QIC's effect changes for wave 1 versus wave 2 participants, who serve as the control group in the first year of the collaborative.
- To further investigate the epidemiology of three ambulatory pediatric diagnostic errors: missed diagnosis of adolescent depression, missed diagnosis of pediatric elevated blood pressure, and delayed diagnosis of actionable laboratory results.
- To evaluate patient outcomes related to these diagnoses including outcomes after positive depression screening, missed elevated blood pressure screening and delayed diagnosis of actionable laboratory values.

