# Methods:

This proposal aims to identify systems solutions for reducing harmful pediatric diagnostic errors. We will perform a prospective, stepped wedge cluster randomized controlled trial to test the hypothesis that QIC strategies can reduce three specific diagnostic errors in a national group of ambulatory pediatric primary care practices. These data will inform future diagnostic errors. Baseline data from the QIC will identify incidence data for errors in 3 separate stages of the diagnostic process: symptoms (missed diagnosis of adolescent depression), signs (missed diagnosis of pediatric elevated blood pressure) and diagnostic tests (delayed diagnosis of actionable laboratory results). Each of these diagnostic errors represents missed opportunities to recognize abnormal diagnostic findings. Human subjects' protection will be completed at the CHAM to cover the researchers and data analysis and at the American Academy of Pediatrics to cover all practices, as completed for prior QuIIN projects.

The goal of this proposal is to reduce diagnostic errors by tracking diagnostic errors rates (outcomes measures) and reliably performing best practices for diagnosing adolescent depression, pediatric elevated blood pressure and actionable laboratory results (process measures). In order to reduce overall data collection burden on practices and to increase engagement of practices that would have been in the control group, we have changed the study design. These changes do not affect the statistical power of the study. The intervention will consist of implementing QIC methodology in all practices to assist teams in reliably performing the processes that will reduce the diagnostic error outcomes via evidence-based tools. Practices will be randomized into three groups, with each group intervening on 1 diagnostic error and serving as the control group for a second diagnostic error. After 8 months of participation, each group will begin intervening on the diagnostic error they were a control group for, continue intervening on their original diagnostic error, and function as the control group for the third diagnostic errors. In the final 8 months of the QIC, all three groups will intervene on all three diagnostic errors.

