Finally, in order to better investigate if reducing these diagnostic errors leads to improved patient outcomes, we will ask practices one time during the 2 year collaborative to identify the time between when the appropriate information to diagnose the patient was available and when the actual diagnosis was conveyed to the family. Practices who have intervened on a given error will track 50 patient charts with one of the following metrics: 1) time between positive mental health screen and diagnosis of depression or depression diagnosis ruled out, 2) the number of days between blood pressure elevation in the medical record and notification of the family, or 3) time between abnormal laboratory result received and notification of family. Additionally, we will ask practices to evaluate 50 patients with a delayed diagnosis of actionable laboratory results 6 months after the diagnostic opportunity to evaluate for emergency department visits, clinic visits, ultimate diagnosis, clinical worsening in laboratory values and other patient morbidities. Similarly, we will ask intervention practices to evaluate 50 patients whose diagnostic instrument of the PHQ-9M was positive 6 months after the diagnostic opportunity to evaluate how many were ultimately diagnosed with depression, attended initial mental health appointments and were referred to mental health or were diagnosed directly by the pediatrician.

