The final set of data will be aggregate data of patients one time during the 2 year collaborative to identify the time between when the appropriate information to diagnose the patient was available and when the actual diagnosis was conveyed to the family. Practices who have intervened on a given error will track 50 patient charts with one of the following metrics: 1) time between positive mental health screen and diagnosis of depression or depression diagnosis ruled out, 2) the number of days between blood pressure elevation in the medical record and notification of the family, or 3) time between abnormal laboratory result received and notification of family, we will ask practices to identify, in the same 50 patients with

a delayed diagnosis of actionable laboratory results 6 months after the diagnostic opportunity to evaluate for emergency department visits, clinic visits, ultimate diagnosis, clinical worsening in laboratory values and other patient morbidities. Similarly, we will ask intervention practices to evaluate 50 patients whose diagnostic instrument of the PHQ-9M was positive 6 months after the diagnostic opportunity to evaluate how many were ultimately diagnosed with depression, attended initial mental health appointments and were referred to mental health or were diagnosed directly by the pediatrician.. This final set of data will be collected only once between 12-18 months after the intervention period begins.

For research and publications that may result from this work, all data will be reported in aggregate, and individual and practice data will not be identifiable. If practice data is presented, each practice will receive an ID number in the report. Potential publications may include a conceptual model of key barriers and potentially useful strategies that emerged from this project. No patients or practice staff will be identified in any report or publication about this study. Practice names will only be used in the acknowledgement section of any potential publication.

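### The one-time outcome chart review is meant to show whether fewer errors improve patient outcomes but names no comparator; for blood pressure and laboratory results the same 50 charts could supply one

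*Combined protocol and SAP*

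**What the plan says.** Under QIC Data Collection and Standardization (section 2, Methods), the reason given for the outcome charts is "in order to better investigate if reducing these diagnostic errors leads to improved patient outcomes". Three timing metrics follow: from positive mental health screen to a depression diagnosis or its exclusion, from elevated blood pressure to telling the family, and from abnormal laboratory result to telling the family. For these, "Practices who have intervened on a given error will track 50 patient charts with one of the following metrics".

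Two 6-month follow-ups are added. For laboratory results, "we will ask practices to evaluate 50 patients with a delayed diagnosis of actionable laboratory results 6 months after the diagnostic opportunity". For depression, "we will ask intervention practices to evaluate 50 patients whose diagnostic instrument of the PHQ-9M was positive 6 months after the diagnostic opportunity".

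Section 7 (Data Collection) repeats the scheme, words the laboratory follow-up as if it used the same set of 50 patients, and ends: "This final set of data will be collected only once between 12-18 months after the intervention period begins".

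The matching secondary objective is worded without any contrast: "To evaluate patient outcomes related to these diagnoses including outcomes after positive depression screening".

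On exposure, Methods has each group intervene on a second error after 8 months and "function as the control group for the third diagnostic errors"; then "In the final 8 months of the QIC, all three groups will intervene on all three diagnostic errors". Wave 2 practices intervene on only two of the three errors.

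**The concern.** Asking whether reducing errors leads to better outcomes requires outcomes under two conditions, with and without the reduction. The plan names one. The timing metrics come from practices that have intervened, and no second set of charts is identified for comparison.

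The laboratory follow-up has a further selection problem. Every patient in it had a late action, so emergency visits or worsening values over 6 months cannot be linked to the delay without patients whose results were handled on time.

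At stake is the only part of the trial that looks past error rates to patients. Notification times and 6-month events would be reported with nothing to set against them, and readers might credit the collaborative for values that were the same before it began. The three primary comparisons are not affected.

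**Working it through.** **1. Is a comparator supplied elsewhere?**
- Table 3 (baseline and monthly review) records depression diagnosis, provider recognition of elevated blood pressure, and whether laboratory action was timely. It does not record days to notification or 6-month outcomes.
- Statistical Models (section 7) gives mixed-effects logistic models for binary outcomes. No model is given for times in days.
- Power Analysis (section 7) covers the three primary outcomes only. There is no stated sample size or precision for the 50-chart data, so there is no plan figure to reproduce.

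**2. Do unexposed charts exist?**
- Elevated readings and abnormal results occur before intervention and in control practices. At the Table 3 rate of 10 charts a month, an 8-month control period yields 10 × 8 = 80 charts, more than the 25 needed. A practice that intervened first on the error has only its pre-intervention charts.
- The collection window is months 12 to 18. One Wave 1 group is still the control for each error until about month 16. After that, Wave 2 practices remain unexposed on their third error.
- Positive screens are different. Universal screening begins with the intervention, so earlier or control charts with a positive screen may be few and selected. The documents give no count.

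**3. What the planned data give.** Inputs: 50 charts per practice; ICC = 0.1, borrowed from the blood pressure and laboratory outcomes in Power Analysis; K practices per metric, assumed. Each practice tracks one metric, so with an even spread K is about 25/3 ≈ 8 (Wave 1 retained) to 40/3 ≈ 13 (with 15 Wave 2 practices).
- 95% CI half-width for one mean = 1.96 × √[(1 + 49 × 0.1)/(50K)].
- K = 8: 1.96 × √(5.9/400) = 0.24 SD. K = 13: 1.96 × √(5.9/650) = 0.19 SD.
- These describe one condition. There is no difference to estimate.

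**4. What a 25/25 split within practice gives.** Charts per condition: 8 × 25 = 200; 13 × 25 = 325. Two-sided 0.05 and 80% power give 1.960 + 0.842 = 2.802. CAC is the cluster autocorrelation between the two periods, assumed 1 to 0.5.
- Detectable difference = 2.802 × √{(2/K) × [(1 − ICC)/25 + ICC × (1 − CAC)]}.
- K = 8, CAC 1: 2.802 × √(0.25 × 0.036) = 0.27 SD.
- K = 8, CAC 0.5: 2.802 × √(0.25 × 0.086) = 0.41 SD.
- K = 13, CAC 1: 2.802 × √(0.1538 × 0.036) = 0.21 SD.
- K = 13, CAC 0.5: 2.802 × √(0.1538 × 0.086) = 0.32 SD.
- If ICC is 0.05 instead, the ranges are 0.27 to 0.35 SD (K = 8) and 0.21 to 0.28 SD (K = 13).

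**5. Concurrent alternative.** With K intervened and K control practices at 50 charts each, detectable difference = 2.802 × √[2 × 5.9/(50K)] = 0.48 SD (K = 8) or 0.38 SD (K = 13). It keeps the randomised contrast but detects only larger differences.

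**6. Laboratory follow-up.** Section 1 puts delay at up to 26%. Finding 50 delayed results then takes at least 50/0.26 ≈ 192 abnormal results; finding 25 takes 25/0.26 ≈ 96, and the other 71 supply the timely group. If the notification and follow-up samples are a single set of 50, splitting by both period and delay leaves 50/4 = 12.5 charts per cell per practice.

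**The case against.** The strongest reply is that the formal objective is descriptive, so one group is enough. That stands for the objective. It does not cover the purpose stated under QIC Data Collection and Standardization, although that is one cautiously worded introductory clause about a one-time secondary collection, in a design changed partly to lighten data collection.

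A reader might infer that all the charts date from after intervention and that a comparison is ruled out. The documents do not say so. They restrict which practices report and when they collect, not the dates of the visits reviewed. Also, the laboratory follow-up in that section is asked of practices without qualification. What is missing is a chart window and a named comparison.

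A reader might also infer that splitting the 50 charts repairs every metric. It does not. It fails for both depression metrics, because screening starts with the intervention. It does not help the laboratory follow-up if the split is by period, because that compares delayed patients with delayed patients.

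Two limits on the remedy also stand. A before-and-after split is open to secular trend, and a calendar term can separate the two only if the practices on a metric start intervening at different times. Delayed versus timely results is not a randomised contrast, and the groups may differ in test mix, since the delay threshold is 30 days for some tests and 7 for others.

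**Conclusion.** The point holds in a limited form. The outcome charts as planned support description, and so meet the secondary objective, but they do not support the comparative purpose given for collecting them. For blood pressure and laboratory notification times, a split of the same charts would give about 200 to 325 charts per condition and detect about 0.27 to 0.41 SD with 8 practices or 0.21 to 0.32 SD with 13.

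Those figures rest on assumptions: practices spread evenly over the three metrics, an ICC taken from other outcomes, and an unknown cluster autocorrelation. They use a normal approximation without a calendar-period term, so they are somewhat optimistic with as few as 8 practices. The matter is a cheap improvement to a secondary collection, not a threat to the trial's main result.

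**What to change.** For blood pressure and laboratory results only:

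1. **Notification times.** State the chart window. Take 25 of the 50 charts from the practice's baseline or control months and 25 from its intervention months. Where possible, also use practices still in control status for that error (Wave 1 until about month 16; Wave 2 on its third error), and draw each metric's practices from more than one randomised group. Analyse with a model suited to times, such as a mixed model on log days or a clustered time-to-event model, with a practice random effect and a calendar-period term.
2. **Laboratory follow-up at 6 months.** Take 25 delayed and 25 timely-action results, matched or stratified by test type, and report the contrast as observational.
3. **Overlap.** State whether the two laboratory samples are one set or two. If one, use only one of the two splits as the design split. If that is the period split, do not restrict the set to delayed patients, or the timely notifications are left out.
4. **Depression.** Keep both depression metrics descriptive, and reword the purpose under QIC Data Collection and Standardization to match.

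If none of this is wanted, rewording the whole purpose as descriptive is an acceptable alternative.

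Cost: the split needs no extra charts, but leaves half as many per condition for description. Charts from control-status practices are extra work unless they replace the metric those practices would otherwise track.

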## 4. Study Population

Our cohort will consist of at least 30 primary care pediatric practices which are part of QuIIN. We are confident that we can obtain this minimum number given that 45 of the 51 QuIIN practices (88%) participating in the pre-survey were interested in participating in a diagnostic error project, and over 300 practices are part of QuIIN from 46 states. We were able to recruit and consent 34 practices, but 9 were lost after randomization due to multiple issues including change in clinic staffing, change in clinic leadership and difficulty with data collection. For this reason we will recruit 15 additional practices to join the collaborative in Wave 2. Interested practices reported seeing between 3,000 and 80,000 pediatric patients per practice annually (median 12,000). No practices will be excluded based on size as even the smallest practices have sufficient patient panels to collect the data described above. Each practice-based team will be multidisciplinary, consisting of at least one physician, nurse and office practice associate allowing for microsystem issues to be transmitted to practice leadership and QI skill to be disseminated across key groups.

#### **Inclusion Criteria**

We will include 30 primary care pediatric practices that are part of the American Academy of Pediatrics' QuIIN organization. Our second wave will recruit 15 additional practices. No practices will be excluded based on race, ethnicity, gender or location.

Given that this study is minimal risk and the data submitted is deidentified, we will request a waiver of consent to look at patients' protected health information submitted by these practices. Patient Protected Health Information (PHI) will not be collected in QIDA.

#### **Exclusion Criteria**

We will not exclude any practices based on gender, race or ethnicity of its providers or patients.

## 4. Participant Recruitment:

Upon IRB approval, primary care clinical teams will be recruited from the membership of the AAP's Quality Improvement Innovation Networks (QuIIN) as well as other AAP listservs. In addition, Expert Group members will assist in recruiting potential practices.

Practices will be enrolled via email and phone solicitation from the 300 QuIIN practices currently involved in the organization. This procedure has been successful in 39 prior and current QuIIN quality improvement collaborative practices. An application packet will be developed that will include a cover letter signed by Drs. [name] and [name] who represent the Project Expert Group. This application packet will also include a project overview, to describe the project and provide specific responsibilities of the practice/individual team members and a link to the application to be completed via Survey Monkey. The application will ask for basic practice information and patient and practice demographics. QuIIN members and others will be notified of the opportunity to participate via email. The application packet includes details about an informational call to be held during recruitment so any interested individual can learn more about the project before completing an application. This informational call will be conducted by Expert Group leadership, AAP QuIIN Staff, and the QI Advisor. This same recruitment format will be applied to the Wave 2 practices.

#### 5. Informed Consent:

The core improvement team (physician, nurse and office associate health care providers) across the 30 Wave 1 practices (25 retained) and 15 Wave 2 practices, enrolled via the AAP's Quality Improvement and Innovation Networks (QuIIN) will be the primary human subjects for this proposal. Each practice will consent for participation via a standardized and previously used QuIIN consent form. Over 300 practices are part of QuIIN from 46 states and have between 1 and 80 providers in each practice. Interested practices reported seeing between 3,000 and 80,000 pediatric patients per practice per year (median 12,000). As the proposal is geared toward improving providers' actions and behaviors to be consistent with best-practice care to diagnose the 3 specific conditions outlined in this proposal, the risk to individual providers is negligible and individual consent will be covered by a waiver of consent. It would be impractical to consult every healthcare provider in every clinic in this study. This consent procedure will be carried out by the American Academy of Pediatrics and QuIIN as in previous projects conducted by their organization. Providers are typically between 30-60 years of age and no participants will be allowed who are less than 22 years old. No provider will be excluded. Similarly, because patients will experience minimal risk and only the minimal personal health information will be collected on patients, will obtain a waiver of consent for patient data. Both of these waivers have been granted on prior QuIIN projects via the AAP's IRB.

## 6. Risk/Benefit:

#### Risks:

The physician, nurse and office associate health care providers at each of the QuIIN practices will be the primary human subjects for this work. As the proposal is geared toward improving providers' actions to be consistent with best-practice care, the risk to providers is minimal. No individual provider compliance data or diagnostic error data will be recorded. Only aggregated data at the practice level is recorded. There will be no additional medical risks in implementing these procedures as they are all standard of care and we are only working to ensure reliable implementation. Providers may feel discouragement if they are unable to reliably perform certain best-practices. In order to minimize this risk, we will provide constant encouragement, utilizing systems focused, blame neutral coaching methodology. Parents and patients will be free to decline any aspect of care as occurs normally in care. As such, no additional risk is posed to the clinic patients.

There are no foreseeable financial risks to patients as a result of this study. Providers could experience a potential decrease in patient volume and therefore financial revenue if their

practice is worse than collaborative baseline and this information is made public. Practices will sign a non-disclosure agreement regarding all data, and QuIIN has never experienced a data breech in 39 prior QIC projects. The research group and QuIIN will work hard to instill this understanding of confidentiality into the collaborative. On the contrary, practices could experience an increase in revenue if patients appreciate improved care and better diagnostic accuracy in their clinics. The financial risks to providers and practices are low.

## **Benefits:**

The potential benefits of this study to the providers include timely and actionable feedback, and alerts to help providers better recognize aspects of diagnostic performance in need of improvement. Teams will have the opportunity to test strategies for improving care that will become a national model, to work with colleagues from around the country, to learn from national experts in decreasing the incidence of diagnostic errors, utilize tools to screen for adolescent depression, high blood pressure and appropriate follow-up with actionable labs, to access practical tools and effective strategies for how to deliver better care, and receive ongoing support for improvement. If improvements in care are achieved, the benefits to parents and children are also likely to be significant. Teams will also have the opportunity to receive coaching from experts in the fields of quality improvement, medical informatics, health IT solutions, pediatric hypertension, pediatric mental health and diagnostic errors. Pending approval, pediatrician participants may have the opportunity to receive Part 4 Maintenance of Certification (MOC) credit if they meet the minimum eligibility criteria.

Although the subjects are the providers, pediatric patients may benefit from this study by being less likely to experience a diagnostic error.

